4.0 Trial Summary

Full title	Helping pregnant smokers quit: Multi-centre RCT of electronic cigarettes and nicotine patches
Short title and/or Acronym	PREP
Trial Design Methodology	Randomised controlled trial
Phase of the Trial	IV
Study Duration	48 Months: 8m for trial set up; 26m for recruitment; 10m to complete remaining treatment and follow-ups (follow-up time-point after 4-week treatment will vary between 5 months-8 months + 1 month to allow follow up of non-responders); 4m for analysis and close-out.
	Expected start date is 1/5/2017. The planned end date of all clinical interventions is 30/5/2020. The planned end date of the whole trial is 30/4/2021.
Study setting	Recruitment: Multi-site – NHS Trial Co-ordinating centre: Health and Lifestyle Research Unit (HAL), QMUL.
Investigational Medicinal Product(s)	Nicotine Transdermal Patches
Medical condition or disease under investigation	Smoking/tobacco addiction
Planned Sample Size	1140
(Maximum) Treatment duration	8 weeks (4 weeks behavioural support + EC/NRT, and 4 further weeks of EC/NRT if requested).
Follow up duration	3 months post-partum
End of Trial definition	The study would be completed and the REC informed, 6 months after the final participant has been followed up for their 3m post-partum follow-up, to allow for saliva sample analysis to be completed.

7.0 List of Abbreviations / Glossary of Terms

AE- Adverse Event

AR- Adverse Reaction

CI- Chief Investigator

CPD- Cigarettes Per Day

CRN- Clinical Research Network

CSO- Chief Scientists Office

CTU- Clinical Trials Unit

DMEC- Data Monitoring and Ethics Committee

EC- E-cigarette

e-CRF- Electronic Clinical Records Form

HAL- Health and Lifestyle Research Unit

IMP- Investigational Medicinal Product

ISF- Investigator Site File

JRMO- Joint Research Management Office

MHRA- Medicines and Healthcare products Regulatory Agency

NIHR- National Institute of Health Research

NRT- Nicotine Replacement Treatment

PI- Principal Investigator

PIS- Participant Information Sheet

QMUL- Queen Mary University of London

RCT- Randomised Controlled Trial

REC- Research Ethics Committee

RM- Research Midwife

RSI- Research Safety Information

SAE- Serious Adverse Event

SAR- Serious Adverse Reaction

SSS- Stop Smoking Services

SmPC-Summary of Product Characteristics

SOP- Standard Operating Procedure

SUSAR- Suspected Unexpected Serious Adverse Reaction

TQD- Target Quit Day

TMF- Trial Master File

TMG- Trial Management Group

TSC- Trial Steering Committee

8.0 Introduction

8.1 Background and study rationale

Smoking in pregnancy: Smoking in pregnancy is associated with increased risks of miscarriage, stillbirth, prematurity, low birth weight, perinatal morbidity and mortality, neo-natal and sudden infant death [1] and possibly also adverse infant behavioural outcomes [2, 3]. In the UK, the annual smoking-attributable maternal and infant health care costs are estimated at £20–£87.5 million [4]. As smoking in pregnancy remains highest amongst socially disadvantaged women [5], eliminating it could reduce socioeconomic inequalities in stillbirths and infant deaths [6]. There is systematic review-level evidence that when pregnant smokers successfully quit, infants' birth outcomes are improved [7] and it is very likely that other morbidities in both mothers and children will be substantially reduced following this crucial health behaviour change [1].

Interventions for pregnant smokers: Finding effective interventions that help pregnant smokers quit has remained elusive so far. Although around 50% of pregnant smokers try quitting [5], spontaneous quit rates in pregnant smokers in the UK are low [8]. Advice by health professionals combined with behavioural support and pharmacotherapy can provide some help, but the effect is limited [9-11]. NIHR and CSO funded several large RCTs to address this problem. An exercise intervention with multi-session behavioural support improved exercise levels but did not help with smoking cessation [12](7% of pregnant smokers achieved abstinence by the end of pregnancy). Financial incentives have shown promising results, but there are practical and ethical issues in applying this approach in routine care [10, 13]. A trial of nicotine patches [14, 15] provided reassuring data on the safety of nicotine replacement in pregnancy, but patches lacked efficacy (9% maintained abstinence to delivery). The two other smoking cessation medications, varenicline and bupropion, include labelling that cautions against use in pregnancy. EC appear to be the most promising of the remaining options, with a realistic chance of providing practical help to pregnant smokers and their children, but no study has tested them in this context so far.

Electronic cigarettes (EC): EC are used with increasing frequency by smokers wishing to limit or stop smoking [16]. EC allow self-titration of nicotine intake [17] and apart from nicotine, they also provide a degree of sensori-motor replacement and enjoyment [18]. This is the most likely explanation of the fact that EC are much more popular among smokers than NRT [16] and generate higher user ratings and better adherence [19].

EC do not contain most of the chemicals responsible for health risks of smoking and those that are present are there at levels much lower than in cigarette smoke [20]. A recent Cochrane review reported no safety concerns over EC use for up to 1.5 years [21]. Some dangers may yet emerge over long-term use, but taking such uncertainty into account, the overall risks are estimated to be some 95% lower than risks of smoking [20]. Although potential population effects of EC, such as a possibility that EC use may renormalize smoking, remain a matter of controversy, there is now a general consensus that EC have a potential to act as treatment for smokers who cannot stop smoking unaided. In cohort studies, promising proportions of hard-to-reach smokers given EC reduced or stopped smoking, including smokers unwilling to quit and smokers with schizophrenia [22-24]. Some UK Stop Smoking Services (SSS) are now using EC and report encouraging results [25, 26]. SSS monitoring data show that smokers using EC have higher cessation rates than smokers using other approaches [26]. Two randomised trials evaluated EC for smoking cessation so far. Both trials used obsolete EC products with low nicotine delivery and in addition, one trial used minimal support [19], while the other concerned smokers unwilling to quit [23]. Despite this, the Cochrane review analysing the trials concluded that EC are an effective treatment [21]. The conclusion is marked as tentative due to the small number of trials, but the uncertainty concerns the size of the effect rather than its direction because EC deliver nicotine and there is ample evidence that NRT is effective [27]. A recent review of reports that evaluated quitting in people who used EC in the past reported a negative result [28], but this was because smokers who were helped by EC have left this population (because they gave up smoking) and only those not helped have remained. Such studies say nothing useful about EC's effectiveness other than that they don't help everyone.

Despite being on the market for only a relatively short time, EC may already be having a population level impact. It is estimated that in the UK some 20,000 smokers are quitting with EC per year who would not have quit otherwise [16].

Use of EC in pregnancy: Pregnant smokers typically use NRT reluctantly, only when asked to do so by their health care providers, but some use EC spontaneously despite the fact that NRT is provided free on the NHS while EC have to be purchased [29, 30]. One of the co-applicants ([name]) surveyed two London SSS over a period of 3 months and found that 25% of pregnant smokers were regularly using EC. In a small survey, a local pregnancy advisor asked ten consecutive pregnant smokers not using EC whether they would consider using EC as an aid to stop smoking. Seven would, two were not sure and one would not. A recent study based on focus groups with 87 pregnant women found that pregnant smokers perceive EC as safer than cigarettes [31]. Finally, [name] is leading an ongoing CRUK study which involves interviewing pregnant and postpartum women about EC. Among 15 women interviewed so far, there is a consensus that EC are considered safer than, and are preferable to, smoking and that the women need more information about EC. A survey of 252 US obstetrician-gynaecologists found that the majority want to know more about the safety and efficacy of EC in pregnancy [32] and commentators have called for trials of efficacy and safety of EC in pregnancy including commentators with anti-EC stance [29, 30]. The results from these independent sources of information are consistent in suggesting that pregnant smokers are likely to be generally open to EC use, and that there is an urgent need for information on EC safety and efficacy in this group.

EC vs NRT in pregnancy: NRT has not shown efficacy in pregnancy, but there are reasons to expect that the barriers to NRT efficacy will be much less detrimental in the case of EC. Pregnant smokers seem to dislike oral NRT products but adherence to nicotine patch use is also very poor [14, 33] e.g. only 7% of women used patches for more than 1 month in the large UK trial [14]. Pregnant smokers may be finding patch use by itself unrewarding as the patches provide nicotine slowly without any immediate feedback or sensorimotor reinforcement. Interestingly, pregnant smokers seem to experience more severe cigarette withdrawal and cravings than other adults [34]. This could be related to stress and/or metabolic changes in pregnancy. Finally, pregnant women metabolise nicotine faster than other smokers and may need higher nicotine doses delivered at a faster rate than standard NRT formulations provide [35].

In contrast to NRT products, EC provide a degree of sensori-motor replacement for smoking and a degree of enjoyment [18]. They also allow extensive individualisation (of flavour, ease of use, and other product characteristics). Regarding nicotine delivery, EC remain inferior to cigarettes, but they deliver nicotine faster than nicotine patches and oral NRT products [36] and unlike patches, they allow for titration of nicotine intake to smokers' needs. These characteristics make it likely that pregnant smokers will adhere to EC treatment much better than to NRT treatment, possibly even magnifying this effect observed with other smokers (in the randomised trial comparing patches and EC, adherence to EC was over three times higher than adherence to patches – [19]). Pregnant smokers using EC are also likely to obtain more adequate nicotine replacement levels and withdrawal relief.

Despite being more palatable than NRT and providing better nicotine replacement, EC deliver lower levels of nicotine than cigarettes, do it much more slowly, and do not include other chemicals contributing to the addictiveness of cigarettes. Even enthusiastic EC users report much lower levels of dependence on EC than they experienced with cigarettes [37]. The National Centre for Smoking Cessation Training (NCSCT) midwifery guidance considers vaping (EC use) in pregnancy better than smoking [38].

In summary, there is a strong rationale for testing the efficacy of EC as a stop-smoking treatment for pregnant smokers. This is an important group for whom few practicable and effective interventions exist. EC have a theoretical potential to be of help and are already used by some pregnant smokers. Finding out whether EC do help is an important priority.

8.2 Assessment and management of risk

Safety of EC in pregnancy: A trial of EC in pregnancy raises safety concerns, which need to be addressed. Such concerns can be divided into concerns about safety of nicotine and safety of other EC ingredients.

Concerns about safety of nicotine in EC are the same as concerns about safety of nicotine in NRT. Pregnant smokers already consume nicotine from cigarettes at doses that are higher than those provided by NRT (and EC [20]). There is a consensus that NRT is much safer than smoking in pregnancy and NRT is universally used by UK pregnancy stop-smoking services [39]. In addition to this, the only RCT which has monitored infant outcomes after nicotine patch use in pregnancy has demonstrated better infant development at two years amongst children born to women randomised to NRT than those randomised to placebo [15], suggesting that nicotine may not in fact pose any major harm to the foetus. The smoking-attributable foetal harm is likely caused by products of tobacco combustion such as carbon monoxide and chemicals such as polycyclic aromatic hydrocarbons which are strongly associated with reduced foetal growth in utero [40] and which are virtually absent in both NRT and EC.

Regarding adverse effects of other chemicals in EC aerosol, the main components of EC liquid are propylene glycol, which is approved for use in pregnancy (e.g. in asthma inhalers) and glycerine, which has no known adverse effects, e.g. glycerine syrup not considered to pose risks in pregnancy. EC are used by millions of smokers and pose little risk over short-term use (up to 1.5 years) [21]. To our knowledge, no chemicals other than nicotine have been identified that would be inhaled by vapers (EC users) in quantities likely to affect the health of the foetus.

Users sometimes report coughing and one EC user was reported to develop transient lipoid pneumonia [41] which was attributed to glycerine-based oils in e-liquid. This is unlikely though, because glycerine is an alcohol and not a lipid. A coincidence is a more likely explanation as no other such cases were identified.

As with all lithium batteries, e.g. in mobile phones and laptops, instances were reported where EC batteries overheated or exploded. This was mostly with use of wrong chargers or DIY modifications. It is important that users receive adequate instructions on battery use and that the chargers are CE marked and compatible with the device used. (The proposed trial would use devices that comply with the latest British Standards and Electrical Equipment Safety Regulations). A trial of EC use in pregnancy would, of course, have to include close monitoring of all adverse events and also of pregnancy outcomes. We would use a similar approach to that applied in the study by Coleman et al [14] (see 'Pharmacovigilance' section for a detailed account of which adverse events will be monitored).

In summary, there are some safety concerns, particularly regarding nicotine, but they are tempered substantially by the fact that EC are not used de novo, but as a replacement for cigarettes and that cigarette smoke contains numerous other chemicals responsible for foetal harm and are vastly more risky on all counts, including the fire hazard. The trial would, of course, closely monitor any adverse events. It is highly unlikely that over short-term use EC would prove more harmful than NRT, but in the event of any unexpected harms, the trial would be stopped. Such a negative result would, in fact, be of significant value. EC are currently being used by an increasing proportion of pregnant smokers. If such use involves an unacceptable degree of risk, evidence of this would have important practical implications.

Safety of nicotine transdermal patches in pregnancy:

The points above regarding nicotine in pregnancy apply to use of nicotine patches in pregnancy as well. In the UK, nicotine skin patches are currently used routinely with pregnant smokers across the Stop-Smoking Specialist Services.

This trial has been categorised as a Type A, low risk Clinical Trial of an Investigational Medicinal Product (CTIMP) Nicotine patches constitute the IMP, and will be used on-label. The EC is a consumer product regulated under the Tobacco Products Directive (TPD). We will be providing a TPD-approved EC starter pack to participants (see intervention details), but they will be able to purchase a different EC and/or e-liquid if the

one provided does not work for them. This is the current approach by stop-smoking services (e.g. Leicestershire, Bristol and the City of London SSS) who provide EC starter packs as part of standard care and encourage clients to switch to other EC products if needed.

9.0 Trial Flowchart

The research team and routine care staff will identify potential participants and provide them with study information and an appointment for the screening and randomisation visit, which can coincide with routine hospital visits.

Screening and randomisation visit with the research team

Informed consent, baseline data, estimated date of delivery and saliva samples will be collected. Women will be randomised to use either nicotine patches or EC. The research team will explain the allocated treatment and will then set a day and time for the participant to receive their first call by the stop smoking advisor.

Experimental Group (n=570)

Queen Mary (QM) team will post: an EC starter-kit and the initial 2 week supply of e-liquid with instructions on use

Phone calls pre-TQD, on TQD, 1, 2, 3 and 4 weeks post-TQD by QM team

smoking status

behavioural support including setting a target quit date (TQD), advice on coping with withdrawal discomfort and tempting situations

monitoring EC and any other treatment use adverse events

further EC supplies posted as needed

At end of pregnancy (35 weeks-10 weeks post-partum)

by QM team:

participants contacted by telephone smoking status

EC and any other treatment use

adverse events

saliva samples for anabasine and cotinine analysis (if abstinent, 'dual-user' or reduced smoking by 50%) provided via mail

by research team: birth and maternal outcomes

3 months post-partum by QM team

Participants contacted by telephone to report any serious adverse events (mother and baby) since delivery and their smoking status.

Control Group (n=570)

QM team will post:

an initial 2 week supply of 15mg/16hr nicotine patches with instructions on use

Phone calls pre-TQD on TQD, 1, 2, 3 and 4 weeks post-TQD by QM team

smoking status

behavioural support including setting a TQD, advice on coping with withdrawal discomfort and tempting situations

monitoring patch and any other treatment use adverse events

further patch supplies posted as needed

At end of pregnancy (35 weeks-10 weeks post-partum) by QM team

by QM team:

participants contacted by telephone smoking status

EC and any other treatment use

adverse events

saliva samples for anabasine and cotinine analysis (if abstinent, 'dual-user' or reduced smoking by 50%) provided via mail

by research team: birth and maternal outcomes

3 months post-partum by QM team

Participants contacted by telephone to report any serious adverse events (mother and baby) since delivery and their smoking status

10.0 Trial Objectives and Design

10.1 Primary Objective/s

To assess long-term (end of pregnancy) efficacy of electronic cigarettes (EC) compared to efficacy of nicotine transdermal patches when used to help pregnant smokers stop smoking.

10.2 Secondary Objective/s

To assess safety of electronic cigarettes (EC) compared to safety of nicotine transdermal patches when used to help pregnant smokers stop smoking; to assess effects of the two interventions on changes in smoke intake and in nicotine intake, effects on short-term abstinence; and adherence to each treatment.

10.3 Endpoints

10.3.1 Primary Endpoint

Prolonged abstinence from smoking from two weeks after the Target Quit Date (TQD) until the end of pregnancy defined as per Russell Standard (up to five lapses allowed with no smoking at all during the previous week at the time of final follow-up [42] and validated by salivary cotinine (< 15 ng/ml [42]) for those not reporting using any nicotine product and anabasine (< 1 ng/ml [43]) for those reporting other forms of nicotine use.

Many pregnant smokers who abstain during pregnancy return to smoking after the delivery. To collect data from the period when smoking is affecting the foetus and minimise the post-delivery relapse effect, we will make the first follow-up call at week 35. Given the likelihood that some women will only be reached after repeated attempts and that longer followed periods have generated high follow-up rates in the previous trials, we will allow a further ten week period to reach participants. If a participant is reached post-delivery, we will also record smoking status prior to the delivery.

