Electronic cigarette: The study will use a TPD-approved refillable EC (Innokin Endura T18; TPD product ID: 00132-16-00001) with a tobacco flavoured e-liquid with nicotine content of 18mg (fruit flavour e-liquid will be offered in cases where participants dislike the tobacco flavour). EC are a consumer product and this is an open label trial and so there are no special labelling or packaging requirements. Each person will be dispensed the starter kit with an initial supply of e-liquid and offered further supplies over the phone for up to 8 weeks. Supplies will be sent via recorded delivery.

Dose modifications: Participants who find their products too strong will be offered 10mg nicotine patches or 11mg eliquid.

Weekly phone calls:

Participants will receive guidance on using their allocated product and support in preparation for the Target Quit Date (TQD), on the TQD, and weekly for four weeks thereafter (6 calls in total). The schedule and content of calls will follow the established protocols of pro-active telephone counselling for smokers (e.g. [44]). This support addresses issues such as planning for the quit day and how to deal with difficult situations, such as others smoking around the quitter. We will also collect smoking status and monitor use of EC and NRT and any other stop smoking medications, and adverse events. Study staff will also complete the study questionnaires with the participants.

End of pregnancy phone call (35 week gestation to ten weeks post-partum)

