12.8.4 Follow up Procedures

Participants will be contacted for 2 data collection follow up calls post intervention; one at the end of pregnancy (35 week gestation to ten weeks post-partum) and the other 3 months post-partum. Participants will be sent a text message a few days before the call is due to ask for a suitable time to call. The QM team will attempt telephone contact first. If this is unsuccessful, participants will also be contacted via text, email and letter. There may also be the opportunity for the research team at the local site to see the participant at the clinic or to arrange a home visit. If the participant is agreeable to this, the research team will collect the follow up questions and return the saliva sample.

At three months post-partum, the study team will make 3 telephone attempts to contact the participant to collect further safety and outcome data.

Preventing distress: Many women who miscarry can participate in follow up without upset; however, calls can occasionally be distressing (e.g. relatives answering after maternal death). We will not routinely exclude women who have miscarried from follow up, but the following will minimise potential distress. The co-ordinating trial office will send the local research teams a list of participants to be followed up within the next fortnight; the local research team will be asked to identify anyone they either know to have or whose medical records show them to have experienced an event which might make follow up distressing. The opinions of the local research team will be considered when deciding whether or not to attempt follow up. In addition to this, a text reminder will be sent to all participants the day before their follow up call is due. Participants may then text back if they do not wish to be called. A reminder text will also allow participants to schedule a convenient time for their call. Participants will be able to text back their smoking status if a call is not convenient.

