17.5 Primary outcome analysis

The primary outcome will be prolonged abstinence reported throughout pregnancy as per Russell Standard (RS) criterion of abstinence [42] (smoking no more the five cigarettes from 2 weeks post-TQD, with no smoking at all over the previous week at end of pregnancy) and validated biochemically at end of pregnancy by salivary cotinine levels of <15 or salivary anabasine levels of <1 ng/ml in participants using nicotine containing products at the time. Participants lost to follow-up or anyone with missing smoking status data for any reason at follow-up, will be classified as smokers. We will compare e-cigarette and NRT treatment groups, using logistic regression. We will conduct sensitivity analysis using the Hedeker method to explore alternative assumptions about the missing data. Full detail on analysis will be provided in the Statistical Analysis Plan.

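### The primary endpoint runs to the end of pregnancy, but its 7-day no-smoking test is tied to a contact that can fall up to ten weeks post-partum, and the recorded pre-delivery status has no stated use

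*Protocol*

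**What the plan says.** **Target.** Section 10.3.1 defines the endpoint as "Prolonged abstinence from smoking from two weeks after the Target Quit Date (TQD) until the end of pregnancy". The primary objective (10.1) also refers to the end of pregnancy, and the sample size (17.1) uses an 8% control quit rate at delivery.

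**7-day test.** Section 10.3.1 requires "no smoking at all during the previous week at the time of final follow-up". Section 17.5 words it as "with no smoking at all over the previous week at end of pregnancy".

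**Validation.** Under 17.5 the outcome is "validated biochemically at end of pregnancy by salivary cotinine levels of <15 or salivary anabasine levels of <1 ng/ml". Section 12.8.1 asks for saliva at the end-of-pregnancy call from women who report abstinence, a reduction of at least half, or smoking alongside NRT or EC.

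**Contact window.** Section 12.8.1 heads the contact "End of pregnancy phone call (35 week gestation to ten weeks post-partum"; 12.8.4 has "one at the end of pregnancy (35 week gestation to ten weeks post-partum"; the flowchart in 9.0 gives the same limits. Section 10.3.1 places the first call at week 35 and adds: "we will allow a further ten week period to reach participants".

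**Relapse after delivery.** Section 10.3.1 recognises that many women return to smoking after delivery and gives this as the reason for the early first call. It adds: "If a participant is reached post-delivery, we will also record smoking status prior to the delivery".

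**Another use of the term.** Section 10.6 applies *final follow up* to the contact at 3 months post-partum.

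**The concern.** The quantity of interest is abstinence while smoking can still affect the foetus. The stated rule tests a different week for any woman first reached after delivery. Take a woman who abstains to delivery, relapses, and is reached eight weeks later. She fails the 7-day test in 10.3.1 as written. She may or may not meet the smoking history in 17.5, depending on what *end of pregnancy* means there. Her recorded pre-delivery status would answer the question, but nothing in the protocol says what it decides. Two analysts could classify her differently.

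At stake are the meaning of the primary result (abstinence in pregnancy, or that mixed with early post-partum relapse), some power, and a classification that could be chosen after the data are seen in an open-label trial.

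**Working it through.** **1. Reproduce the plan's own figures (17.1).** Inputs: 8% v 14%, 570 per arm, two-sided alpha 0.05.

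Power = Φ[(p1 − p0 − 1.96·SE0)/SE1], where SE0 = √[2p̄(1 − p̄)/n] and SE1 = √{[p0(1 − p0) + p1(1 − p1)]/n}.

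- p̄ = 0.11, SE0 = √(0.1958/570) = 0.01853, SE1 = √(0.1940/570) = 0.01845.
- Power = Φ[(0.06 − 0.03633)/0.01845] = Φ(1.283) = 90.0%.
- Solving the same formula for 90% power gives 570 per arm, 1,140 in total, as stated.

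**2. Dilution when both arms behave alike.** Let f be the share of women abstinent to delivery who are first reached afterwards, and r the share of those who have relapsed by then. The protocol gives neither, so both are assumptions. The observed rate is the true rate × k, with k = 1 − f·r.

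| f | r | k | Patch | EC | Risk ratio | Power |
|---|---|---|---|---|---|---|
| 0 | – | 1.00 | 8.0% | 14.0% | 1.75 | 90.0% |
| 10% | 20% | 0.98 | 7.8% | 13.7% | 1.75 | 89.4% |
| 20% | 30% | 0.94 | 7.5% | 13.2% | 1.75 | 87.9% |
| 40% | 30% | 0.88 | 7.0% | 12.3% | 1.75 | 85.5% |
| 50% | 60% | 0.70 | 5.6% | 9.8% | 1.75 | 75.9% |

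The factor k cancels from the risk ratio. The cost is power and a lower absolute difference, not bias in the ratio.

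**3. What a difference between arms would do (conditional only).** Suppose the true rate is 8% in both arms, so each observed rate is 8% × (1 − f·r).

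- 35% v 45% reached late, r = 30%: 7.16% v 6.92%, a spurious 0.24 points; type I error 5.3%.
- 30% v 50%, r = 30%: 7.28% v 6.80%, 0.48 points; 6.2%.
- 20% v 50%, r = 40%: 7.36% v 6.40%, 0.96 points; 9.8%.

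**4. Window length.** Counted from the first call, week 35 + 10 = week 45. For a birth at week 40 (assumed) that is 45 − 40 = 5 weeks post-partum; for births at weeks 37 and 42 it is 8 and 3 weeks. Sections 9.0, 12.8.1 and 12.8.4 all give ten weeks post-partum. Section 10.3.1 does not name the starting point of its ten weeks, so the two statements may or may not agree.

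**5. What saliva can show.** A sample given after delivery reflects smoking at that time. It cannot confirm the pre-delivery status of a woman who has since relapsed. Changing the wording of the 7-day test does not remove this limit.

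**The case against.** **The two sections may mean the same thing.** Because *end of pregnancy* names the contact running to ten weeks post-partum, the week in 17.5 can be read as the week before that contact, as in 10.3.1. This stands, so I do not call it a flat contradiction. But on that reading both sections test a week that can fall after delivery, which moves away from the stated target.

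**The power loss comes from validation, not wording.** This largely stands. If saliva remains required, women who have relapsed by a late call stay non-abstinent in the primary analysis, and re-anchoring recovers almost none of the loss there. What it gains is a defined endpoint and a sensitivity analysis on the intended quantity.

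**The assumed inputs may be high.** Section 17.10 expects successful quitters to be keen to attend, so abstainers may be reached earlier than average. Some dilution may also already sit in the 8%, which 17.1 extrapolates from earlier trials. Neither can be checked here.

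**These are matters for the SAP.** Sections 17.3 and 17.5 do defer analysis detail to it. The definition of the primary endpoint, however, is fixed in the protocol, and its anchor is misplaced there.

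**Two stronger readings are not supported.**

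- A reader might infer that the result is biased. Follow-up procedures are the same in both arms (9.0, 12.8.4), and nothing shows that contact timing differs. The open-label design makes a difference possible, no more.
- A reader might infer that women whose pregnancy ends early become smokers by rule, because the window opens at week 35. Section 17.5 so classifies only those lost to follow-up or with missing status. Section 12.8.4 says women who miscarry are not routinely excluded from follow-up, and nothing bars earlier contact.

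**Conclusion.** The point holds as a misplaced anchor in the primary endpoint, of moderate severity. That part needs no assumption: the target is the end of pregnancy, the operative test can fall ten weeks later, and the status recorded to bridge the gap has no stated use. The term *final follow-up* is also loose, since 10.6 gives that name to the 3-month call.

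The size rests on assumed inputs. With equal timing and relapse in both arms, and 20% to 40% of abstainers reached late with 30% of those relapsed, power falls from 90.0% to between 87.9% and 85.5%, with the risk ratio unchanged. The wider grid runs from 89.4% to 75.9%. The type I error figures apply only if timing or relapse differs by arm, which the protocol does not show; they are a reason to tabulate timing, not evidence of bias.

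**What to change.** 1. **One definition in 10.3.1 and 17.5.** The previous week is the 7 days before the end-of-pregnancy call if the woman is still pregnant, and otherwise the 7 days before the pregnancy ended. Replace the reference to final follow-up with this wording.
2. **Use the recorded status.** Let pre-delivery status decide the secondary endpoint of self-reported prolonged abstinence at end of pregnancy.
3. **Keep saliva validation for the primary.** Women who have relapsed by a post-partum call stay non-abstinent there. State openly that the primary therefore still includes some post-partum relapse.
4. **One pre-specified sensitivity analysis.** Count women abstinent to delivery by self-report as abstinent.
5. **One table by arm.** Show contact before or after delivery, and weeks post-partum.
6. **One window.** Reconcile the ten-week period in 10.3.1 with the ten weeks post-partum elsewhere, and state that contact opens at week 35, or at the end of pregnancy if earlier.

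The cost is protocol wording, one analysis and one table. The sample size does not change. No new measurement is needed, because pre-delivery status (10.3.1) and date of birth (12.8.1) are already collected.
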